## 5 SAFETY PARAMETERS

Safety variables include incidence of AEs (or TEAEs), laboratory test results and vital signs.

### 5.1 Adverse Events

An AE is any untoward medical occurrence associated with the use of a drug in humans, whether or not considered drug related. This includes the following:

- Any clinically significant worsening of a pre-existing condition.
- Note: Emergence of a new pathogen associated with a clinical event during therapy at a site other than the initial site of infection will be considered to be an AE.
- Any recurrence of a pre-existing condition.
- An AE occurring from overdose of a Sponsor study drug whether accidental or intentional (i.e., a dose higher than that prescribed by a health care professional for clinical reasons).
- An AE occurring from abuse of a Sponsor study drug (i.e., use for nonclinical reasons).
- An AE that has been associated with the discontinuation of the use of a Sponsor study drug.

Note: A procedure is not an AE, but the reason for a procedure may be an AE.

A pre-existing condition is a clinical condition (including a condition being treated) that is diagnosed before the patient signs the ICF and that is documented as part of the patient’s medical history.

The questions concerning whether the condition existed before the start of the active phase of the study and whether it has increased in severity and/or frequency will be used to determine whether an event is a treatment-emergent AE. An AE is considered to be treatment-emergent if (1) it is not present when the active phase of the study begins and is not a chronic condition that is part of the patient's medical history, or (2) it is present at the start of the active phase of the study or as part of the patient's medical history, but the severity or frequency increases during the active phase. The active phase of the study begins at the time of the first dose of the study drug. The active phase of the study ends at the Follow-up/EOS.

Treatment-emergent AEs will be identified in the eCRF Form "Adverse Event" if the answer to the question "Did the AE start after the patient took the first dose?" is answered as Yes.

The Investigator will make a determination of the relationship of the AE to the study drug using a four-category system according to the following guidelines:

- Not related: when the AE is definitely caused by the patient's clinical state, or the study procedure/conditions.
- Unlikely Related: when the temporal association between the AE and the drug is such that the drug is not likely to have any reasonable association with the AE.
- Possibly Related: when the AE follows a reasonable temporal sequence from the time of drug administration but could have been produced by the patient's clinical state or the study procedures/conditions.
- Related: when the AE follows a reasonable temporal sequence from administration of the drug, abates upon discontinuation of the drug, follows a known or hypothesized cause-effect relationship, and (if appropriate) reappears when the drug is reintroduced.

Related to study treatment will be identified as possibly related or related as per reported on eCRF Form "Adverse Event".

## 5.2 Serious Adverse Events

An SAE is any AE occurring at any dose that meets 1 or more of the following criteria:

- Results in death;
- Is life-threatening;
- Requires patient hospitalization or prolongation of an existing hospitalization;
- Results in persistent or significant disability or incapacity;
- Results in a congenital anomaly or birth defect;
- Results in an important medical event.

## 5.3 Laboratory Parameters

Laboratory evaluations are done at screening, Day 10 and follow-up visit 2 (Day 28). Additional clinical laboratory evaluations will be performed at other times if judged to be clinically appropriate or if the ongoing review of the data suggests a more detailed assessment of clinical laboratory safety evaluations is required.

Hematology laboratory tests include: hematocrit (L/L), hemoglobin (g/L), MCH (pg), MCHC (g/L), MCV (fL), Platelet count (G/L), RBC count (T/L), WBC count (G/L) and WBC differentials (Neutrophils, Eosinophils, Basophils, Lymphocytes and Monocytes) in both percent (%) and absolute (G/L).

Biochemistry laboratory tests include: albumin (g/L), alkaline phosphatase (U/L), ALT (U/L), AST (U/L), bicarbonate (mmol/L), BUN (mmol/L), calcium (mmol/L), chloride (mmol/L), cholesterol (mmol/L), creatinine (umol/L), GFR CKD-EPI (mL/min/1.73m^2), GGT (U/L), glucose (mmol/L), LDH (U/L), phosphorus (mmol/L), potassium (mmol/L), sodium (mmol/L), total bilirubin (umol/L), total protein (g/L), triglycerides (mmol/L) and uric acid (umol/L).

#### 5.4 Other Safety Parameters

Pulse oximetry and saturation measurements will take place on screening, Days 1, 3, 5, 7, 10, follow-up visit 1 (Day14) and follow-up visit 2 (Day28/EOS).

### 6 STATISTICAL METHODOLOGY

#### 6.1 Determination of Sample Size

As per protocol, it was anticipated that 208 patients will be randomized into the study in a 1:1:1:1 ratio to 900, 1800, or 3600 mg dalcetrapib or placebo. The original sample size was calculated for the sustained resolution endpoint and was described in the protocol as follows: The purpose of the proof-of-concept study is to identify whether there is sufficient promise of efficacy to justify conducting a Phase 3 study in a larger sample size and to determine efficacious dose to be used in Phase 3. While the entirety of data will be considered at the end of study, the sample size has been chosen to ensure that a positive trend will be present with alpha of 0.2 when considering the two highest doses combined compared to placebo. One-hundred twenty-seven (127) resolution events provides 80% power to demonstrate a positive trend if the average hazard ratio (HR) of the two dalcetrapib groups is 1.4 relative to placebo. Allowing for 20% of patients not resolving, 156 patients (52 per treatment arm) will be enrolled across the two highest dose levels and placebo arms, and an additional 52 will be randomized to 900 mg for a total sample size of 208 patients.

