## **8. SAMPLE SIZE AND DATA ANALYSES**

### **8.1. Determination of Sample Size**

The purpose of the proof-of-concept study is to identify whether there is sufficient promise of efficacy to justify conducting a Phase 3 study in a larger sample size and to determine efficacious dose to be used in Phase 3. While the entirety of data will be considered at the end of study, the sample size has been chosen to ensure that a positive trend will be present with alpha of 0.2 when considering the two highest doses combined compared to placebo. One-hundred twenty-seven (127) resolution events provides 80% power to demonstrate a positive trend if the average HR of the two dalctetrapib groups is 1.4 relative to placebo. Allowing for 20% of patients not resolving, 208 patients (52 per treatment arm) will be enrolled. One interim analysis will be conducted once 97 resolution events have occurred to allow 73 resolution events to have occurred in the two highest dose levels and placebo arm. At the interim analysis, if the average HR of the two highest dose levels relative to placebo is greater than 1.45, the study will stop due to efficacy and the program will be able to proceed directly to Phase 3. At the interim analysis, if the average HR of the two highest dose levels relative to placebo is between 1.0 and 1.45, the study will continue enrollment until 169 resolution events have occurred. At the interim analysis, if the average HR of the two highest dose levels is less than 1.0, the study will be stopped for lack of efficacy. The final analysis will be performed at an alpha of 0.186. These boundaries were determined by setting the efficacy boundary to follow the power family boundary with  $\rho=2$  and the futility boundary is manually set to HR=1.

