### **4 EFFICACY ENDPOINTS**

#### **4.1 Primary Efficacy Endpoint**

The primary efficacy endpoint is:

- Time to sustained clinical resolution of symptoms (excluding cough, sense of smell and taste)

Sustained clinical resolution is defined as occurring when no key COVID-19 related symptom (excluding cough, sense of smell and taste) has a score higher than 1 over a 72-hour period (as documented using an electronic patient-reported outcome [ePRO] instrument or in the eCRF). The time to resolution will be taken as the time from randomization until the first day of the last 72-hour period where the patient meets the definition of resolution within 28 days. Patients who do not meet the definition of resolution 28 days after randomization will be considered not resolved.

The classification of sustained clinical resolution of symptoms (excluding cough, sense of smell and taste) follows similar steps as the algorithm presented in Appendix 1.

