#### 6.2 Statistical Considerations

Continuous variables will be summarized by the standard descriptive statistics: number of patients (n), mean, standard deviation, median, Q1, Q3, minimum, and maximum, along with confidence interval (CI) for outcome measures when appropriate. Frequency of patient or events and percentages will be summarized for categorical variables, again with CI when appropriate. Time to event variables will be summarized using Kaplan-Meier methods.

All statistical tests will be conducted at a two-sided 0.20 significance level.

Statistical analyses will be performed using SAS Version 9.4 or higher.

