### **6.2.1 Interim Analysis**

The study will be overseen by an independent Data Monitoring Committee (DMC). The DMC will review safety data throughout the study. The DMC will review efficacy data at the interim analysis and at the end of the study. A DMC Charter, which includes detailed processes, will be prepared.

One interim analysis will be conducted for efficacy once 120 patients with a follow-up of 28 days have occurred. No decision to stop the trial will be made based on these efficacy findings as the review of data will occur around the time the last patients enrolled in the study complete the treatment period.

The members of the committee will include appropriately qualified medical personnel, and other members, as required. Detailed responsibilities of the DMC will be provided in the DMC Charter.

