##### **6.4.1 Primary Analysis**

The primary endpoint is time to sustained clinical resolution of symptoms (excluding cough, sense of smell and taste) as determined by symptom score. Sustained clinical resolution of symptoms (excluding cough, sense of smell and taste) is defined in Section 4.1. Time to sustained clinical resolution will be calculated as date of resolution – date of randomization + 1. Subjects who did not resolve will be censored at the last time point where they were not resolved [see Section 9 Appendix 1]. The number and percentage of patients whose symptoms resolved will be presented, and to summarize the time to resolution, censored subjects will be imputed with a time to resolution of 29 days and simple medians with 80% confidence intervals will be provided.

The differences in time to sustained clinical resolution of symptoms (excluding cough, sense of smell and taste) between the treatment groups will be evaluated using 2-sided log-rank tests. The combined two highest treatment groups will be compared to placebo in addition to the comparison of individual doses.

The cumulative incidence curve for sustained clinical resolution (excluding cough, sense of smell and taste) will also be presented using 1 – Kaplan-Meier estimates(Section 7, Figure 2). Should there be several deaths, the cumulative incidence curve will be presented under a competing risk model.

A listing with the score of each symptom at each time point will be provided (Section 7, Listing 7).

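### The 80% power in SAP 6.1 is a one-sided 0.20 figure; at the SAP's two-sided 0.20 level, 127 events give about 69% power for HR 1.4

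*SAP*

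**What the plan says.** SAP 6.1 sizes the comparison of the two highest doses combined with placebo at an alpha of 0.2, without a side, and states that "127) resolution events provides 80% power to demonstrate a positive trend if the average hazard ratio (HR) of the two dalcetrapib groups is 1.4". It allows for 20% of patients not resolving and plans 156 patients in those three arms. Protocol 8.1 and the synopsis give no side either.

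The tests themselves are two-sided. SAP 6.2: "All statistical tests will be conducted at a two-sided 0.20 significance level". SAP 6.4.1: differences "between the treatment groups will be evaluated using 2-sided log-rank tests", and "simple medians with 80% confidence intervals will be provided". Protocol 8.4.1.1 also specifies a two-sided log-rank test.

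Protocol 8.1 describes one look at 73 events in the three arms, an efficacy bound of HR 1.45 from the power family with rho = 2, and futility at HR 1. It adds: "The final analysis will be performed at an alpha of 0.186". SAP 6.2.1 changes this: "No decision to stop the trial will be made based on these efficacy findings".

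On the endpoint, SAP 6.1 says: "The original sample size was calculated for the sustained resolution endpoint". The primary endpoint in SAP 4.1 is now "Time to sustained clinical resolution of symptoms (excluding cough, sense of smell and taste").

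**The concern.** Read together, SAP 6.1 and 6.2 suggest 80% power at two-sided 0.20. If the calculation was one-sided, the planned test has less power than the only figure the reader is given. SAP 6.1 says the study is meant to judge whether there is enough promise to justify Phase 3. A non-significant combined-dose result counts as stronger evidence against HR 1.4 if the test is believed to have 80% power than if it has less. The SAP also changed the interim rule and the primary endpoint, and it gives no power under the new rules.

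**Working it through.** **Inputs.** 127 events, HR 1.4, alpha 0.2, 80% power, 1:1:1:1 randomisation and 156 patients in three arms (SAP 6.1). Interim at 73 events, rho = 2, efficacy bound HR 1.45, futility HR 1, final alpha 0.186 (protocol 8.1). Two-sided 0.20 (SAP 6.2). No stopping (SAP 6.2.1).

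**Formula.** Two doses against placebo is 2:1 allocation, so the log-rank information (Schoenfeld) is D × 2/3 × 1/3 = D × 2/9. The mean of Z is ln(1.4) × √(D × 2/9), with ln(1.4) = 0.3365.

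**Step 1: reproduce the protocol's figures.** The alpha spent at the look is total × (73/127)². The bound on the HR scale is exp(z₁ / √(73 × 2/9)). The final critical value is solved with non-binding futility. Power is P(Z₁ > z₁) + P(0 < Z₁ < z₁, Z₂ > z₂) at HR 1.4.

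| | Stated | One-sided 0.20 | 0.10 per side |
|---|---|---|---|
| Alpha spent at look | – | 0.0661 | 0.0330 |
| z₁ | – | 1.506 | 1.838 |
| Interim HR bound | 1.45 | 1.453 | 1.578 |
| Final nominal alpha | 0.186 | 0.1862 | 0.0897 per side (0.179 two-sided) |
| Power, 127 events | 80% | 80.0% | 67.6% |

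The one-sided column matches all three stated figures; the other column matches none. If futility is treated as binding with 0.10 per side, the doubled final alpha is 0.185, which is close to 0.186. The bound is still 1.578, however, and the power is 68.1%, so that reading also fails.

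**Step 2: power of the SAP's own test.** With no stopping, the final test is in effect a fixed design. Mean Z = 0.3365 × √(127 × 2/9) = 1.788.

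- One-sided 0.20: Φ(1.788 − 0.842) = 82.8%.
- Two-sided 0.20: Φ(1.788 − 1.282) = 69.4%.

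**Step 3: what 80% would take at two-sided 0.20.**

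- Events: (1.282 + 0.842)² / (0.3365² × 2/9) = 179.2, so 180. At 20% non-resolution that is 180 / 0.8 = 225 patients, against 156 planned.
- HR with 127 events: exp((1.282 + 0.842) / √(127 × 2/9)) = 1.491.

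**Step 4: the current primary endpoint.** Neither document gives a resolution rate for it. As an assumed range over the 156 patients, at HR 1.4 and two-sided 0.20:

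| Resolving | Events | Power |
|---|---|---|
| 60% | 94 | 60% |
| 80% | 125 | 69% |
| 100% | 156 | 76% |

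Even if every patient resolved, power would stay below 80%.

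**The case against.** The strongest reply is that nothing is miscalculated. The 80% is right for the design it describes, the aim of showing a positive trend reads as directional, and SAP 6.1 presents the paragraph as the original calculation taken from the protocol. That is fair as far as it goes. The defect is an unstated side and a power not restated for the SAP's test. But the SAP supersedes the protocol where they differ (SAP 1), and 80% is the only power it offers.

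Second, SAP 1 puts more weight on viral load for the proof-of-concept decision, and no rule ties that decision to a null symptom result. This lowers the stakes but does not correct the figure, and the symptom endpoint is still primary.

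Third, 127 is a planning number and 69% depends on the approximation. Freedman's formula at 127 events, 2:1 and two-sided 0.20 gives 65.4% or 72.4%, depending on the direction in which the HR is expressed. Dropping slow-resolving symptoms could also raise the event count. None of these variants reaches 80%.

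Fourth, the one-sided basis is inferred. A fixed one-sided Freedman calculation needs 128 events, so the 127 need not have come from the two-look design. That point stands on the origin of the number. It does not weaken the case on the side, because that calculation is one-sided too.

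Finally, SAP 6.2, 6.2.1 and 6.2.3 already displace the 0.186 level and the two-sided 0.05 gate of protocol 8.9 by implication. Saying so outright is a convenience.

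**Conclusion.** The concern holds. The protocol's own bound, final alpha and power identify a one-sided total alpha of 0.20. The test the SAP plans is two-sided at 0.20 with no efficacy stopping. For HR 1.4 and 127 events its power is about 69%, so the miss probability is about 31% instead of 20%. This rests on Schoenfeld information, 2:1 allocation, proportional hazards and 127 events in the three arms. Across the assumed resolution rates for the current primary endpoint the power is 60% to 76%. Type I error and the treatment estimate are unaffected; what is wrong is the power a reader would use to weigh a null result. It should be fixed.

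**What to change.** Keep the sample size, the 127 events and the two-sided 0.20 level. After the protocol text quoted in SAP 6.1, add the following, once the sponsor has checked the first sentence against its sizing records:

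> The original calculation used a one-sided total alpha of 0.20 with one interim look. At the two-sided 0.20 level of Section 6.2, without efficacy stopping, 127 resolution events give about 69% power for HR 1.4 and 80% power for HR about 1.49. These figures refer to the original sustained-resolution endpoint; no resolution rate was assumed for the current primary endpoint.

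Also state that the final alpha of 0.186 (protocol 8.1) and the two-sided 0.05 gate (protocol 8.9, at which 127 events give about 43% power) do not apply under this SAP.

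The cost is wording only. No test, interval, event count or sample size changes; the stated power becomes less favourable.

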#### 6.2 Statistical Considerations

Continuous variables will be summarized by the standard descriptive statistics: number of patients (n), mean, standard deviation, median, Q1, Q3, minimum, and maximum, along with confidence interval (CI) for outcome measures when appropriate. Frequency of patient or events and percentages will be summarized for categorical variables, again with CI when appropriate. Time to event variables will be summarized using Kaplan-Meier methods.

All statistical tests will be conducted at a two-sided 0.20 significance level.

Statistical analyses will be performed using SAS Version 9.4 or higher.

### **6.2.1 Interim Analysis**

The study will be overseen by an independent Data Monitoring Committee (DMC). The DMC will review safety data throughout the study. The DMC will review efficacy data at the interim analysis and at the end of the study. A DMC Charter, which includes detailed processes, will be prepared.

One interim analysis will be conducted for efficacy once 120 patients with a follow-up of 28 days have occurred. No decision to stop the trial will be made based on these efficacy findings as the review of data will occur around the time the last patients enrolled in the study complete the treatment period.

The members of the committee will include appropriately qualified medical personnel, and other members, as required. Detailed responsibilities of the DMC will be provided in the DMC Charter.

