#### **4.5. Stopping Rules**

The study will enroll 208 patients (52 patients to each of 900 mg, 1800 mg, 3600 mg and placebo). One interim analysis will be conducted for efficacy once 97 resolution events have occurred to allow 73 resolution events to have occurred in the two highest dose levels and placebo arm. At the interim analysis, if the average HR of the two highest dose levels relative to placebo is greater than 1.45, the study will stop due to efficacy and the program will be able to proceed directly to Phase 3. At the interim analysis, if the HR of the two highest dose levels relative to placebo is between 1.0 and 1.45, the study will continue enrollment until 169 resolution events have occurred. At the interim analysis, if the HR of the two highest dose levels is less than 1.0, the study will be stopped for lack of efficacy. The DMC will issue a recommendation to enroll patients, or to stop the study depending on interim analysis assessment. The DMC may recommend dropping one or more treatment arms. The DMC will continue to review safety and assess the risk/benefit profile on an ongoing basis.

A DMC Charter, which includes detailed processes, will be prepared.

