## **8.7. Interim Analysis**

One interim analyses will be conducted when 97 resolution events have occurred.

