## 2 STUDY DESCRIPTION

### 2.1 Study Design

This is a randomized, double-blind, multicenter Phase 2a proof-of-concept study in outpatients with confirmed, mild to moderate, symptomatic COVID-19. Electronic informed consent must be obtained from all patients or their legally authorized representative during screening before any study-related procedures are performed. The Screening/Baseline assessments may be performed at the study site or as a home visit.

A total of 208 patients will be randomized to receive 900, 1800, or 3600 mg of dalcetrapib or placebo once daily (52 patients to each of 900 mg, 1800 mg, 3600 mg and placebo) for 10 days. Patients will be randomized and receive first dose of study drug within 72 hours of receiving a positive PCR or Point-of-care test for SARS-CoV-2. Patients need to have at least two of the 14 common COVID-19-related symptoms described in the inclusion criteria rated as mild or moderate, as evaluated by ePRO assessment or eCRF. Symptoms will be assessed at each study visit daily for the first 10 days, then at Day 14 and Day 28, and as clinically indicated. Symptoms will be evaluated as absent, mild, moderate, or severe depending on their impact on activities of daily living. SARS-CoV-2 viral loads will be obtained by both saliva (Oragene) collection and mid-turbinate nasal swab self-collection under supervision of a healthcare professional (virtual or home visit) at Screening/Baseline, Day 1, Day 3, Day 5, Day 7, Day 10, and Day 28. Patients who require hospitalization after initiation of study treatment will be followed for safety assessment through Day 28.

The study will be overseen by an independent Data Monitoring Committee (DMC). The DMC will review the safety data throughout the study. The DMC and Sponsor will review efficacy data at the interim analysis and at the end of the study. A DMC Charter, which includes detailed processes, will be prepared. One interim analysis will be conducted once 120 patients have a follow-up time of 28 days.

All patients will be closely monitored for adverse events (AEs) from informed consent for at least 18 days after the final dose of study treatment (until Day 28±2). Patients who withdraw early from the

study treatment will have follow-up phone calls to collect safety data until End of Study on Day 28±2. On days of laboratory assessments and PK sample collection, outpatient subjects may have a home visit.

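### The protocol stops the trial at the interim if the HR is above 1.45 or below 1.0; the SAP moves the look and rules out any efficacy stop, yet withdraws neither those rules nor the power figure built on them

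*SAP*

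**What the plan says.** **Protocol.** Section 8.7 gives the trigger: "One interim analyses will be conducted when 97 resolution events have occurred". The synopsis and sections 3.1.1, 4.5 and 8.1 add that this is meant to yield 73 events in the two highest doses plus placebo, and attach consequences to the result. In 4.5, an interim HR that "is greater than 1.45, the study will stop due to efficacy and the program will be able to proceed directly to Phase 3"; and "if the HR of the two highest dose levels is less than 1.0, the study will be stopped for lack of efficacy". Between 1.0 and 1.45 the trial goes on to 169 events. Section 4.5 has the DMC recommend continuing or stopping on this assessment. Section 8.1 derives the bounds from a power-family boundary with rho = 2 and adds: "The final analysis will be performed at an alpha of 0.186".

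**SAP.** Section 2.1: "One interim analysis will be conducted once 120 patients have a follow-up time of 28 days". Section 6.2.1 repeats that trigger and says: "No decision to stop the trial will be made based on these efficacy findings". Its reason is that the review will fall at about the time the last enrolled patients finish treatment. Section 6.1 reproduces the protocol's sample-size text, including 80% power with 127 events at HR 1.4, but ends before the interim rules. Section 6.2 tests everything at two-sided 0.20. Section 4.1 removes cough, smell and taste from the primary endpoint. Section 1 says the SAP supersedes the protocol where the two differ in descriptions or explanations.

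**The concern.** The two documents give the DMC different triggers and, for some results, incompatible consequences. An interim HR of 1.5 or of 0.95 ends the trial under the protocol and changes nothing under the SAP. The SAP does not mention the 1.45 and 1.0 bounds or the 0.186 level, so it neither keeps nor withdraws them. The bounds were also set for the protocol's endpoint. The SAP's primary endpoint is a different one, so it is not stated which HR a DMC would compare with them.

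Two things are at stake. One is which rule the DMC Charter carries, since both documents leave the detail to a Charter still to be prepared. The other is whether the 80% power repeated in SAP 6.1 describes the trial that the SAP actually analyses.

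**Working it through.** **Inputs.** From Protocol 8.1: alpha 0.2 (sidedness not given there), 127 final events, 80% power, HR 1.4, 73 interim events in the three arms, bounds 1.45 and 1.0, final level 0.186, rho = 2, 20% of patients not resolving. From the synopsis: 1:1:1:1 allocation, so two doses against placebo is 2:1 and each event carries 1/3 × 2/3 = 2/9 units of information. From SAP 6.2: two-sided 0.20. From SAP 6.2.1: 120 patients.

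**Step 1: reproduce the protocol's design.** Take alpha as one-sided 0.2.

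- Information at 73 events is 73 × 2/9 = 16.22, so the SE of log HR is 1/√16.22 = 0.248. At 127 events it is 28.22.
- Alpha spent at the interim is 0.2 × (73/127)² = 0.0661, z = 1.506. The bound is exp(1.506 × 0.248) = 1.453, matching 1.45.
- The remaining alpha, with futility treated as non-binding, gives a final one-sided level of 0.1862, matching 0.186.
- Power at HR 1.4 with both stops applied is 80.0%, matching 80%.

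No other variant tried gives these figures. Fixed designs need 113 events (one-sided, 2:1) or 180 (two-sided, 2:1), and 101 or 160 with 1:1. The same two-look design at 0.10 per side gives a bound of 1.578 and 67.6% power. The 80% therefore belongs to a one-sided 0.20 design that includes the stops.

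**Step 2: how often the protocol rule calls for a stop.** Estimated log HR is taken as normal with mean ln(HR) and SE 0.248. P(efficacy stop) = P(Z > (ln 1.45 − ln HR)/0.248); P(futility stop) = P(Z < −ln HR/0.248).

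| True HR | Above 1.45 | Below 1.0 | Total |
|---|---|---|---|
| 1.0 | 6.7% | 50.0% | 56.7% |
| 1.1 | 13.3% | 35.1% | 48.3% |
| 1.2 | 22.3% | 23.1% | 45.4% |
| 1.3 | 33.0% | 14.5% | 47.5% |
| 1.4 | 44.4% | 8.8% | 53.1% |

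(Totals are from unrounded values.) The total is below 50% for true HR from about 1.07 to 1.35. A Cox simulation (104 against 52 patients, first 73 events, 4,000 runs per HR) gave totals of 55.9%, 49.7%, 47.0%, 49.4% and 53.1%.

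**Step 3: compare the triggers.** Applying the protocol's 20% allowance to the 120 patients alone gives 120 × 0.8 = 96 events, 96 × 3/4 = 72 of them in the three arms, against 97 and 73. The looks carry similar expected information, so the conflict is mainly in the consequence.

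**Step 4: power for the SAP's design.** One final test with 127 events at HR 1.4: ln 1.4 × √28.22 = 0.3365 × 5.312 = 1.787.

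- Two-sided 0.20 (critical z 1.282): Φ(1.787 − 1.282) = Φ(0.506), about 69.4%.
- One-sided 0.20 (critical z 0.842): Φ(1.787 − 0.842) = Φ(0.946), about 82.8%.

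**The case against.** The best defence is that the documents already indicate which text governs. The SAP claims precedence and gives a sensible reason for not stopping: by the time of the review, enrolment is over and dosing nearly so. The protocol's rule is also softer than it sounds, because the DMC issues a recommendation and the 0.186 level reproduces only with non-binding futility (binding futility would give 0.203). SAP 6.1 labels its power text as the original calculation.

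Much of this stands. It supports resolving the conflict in the SAP's favour and lowers the practical stakes. It does not close the gap. A clause about descriptions or explanations may or may not reach a stopping rule on which the DMC is asked to act. Protocol Appendix 3 requires IRB/EC approval before changes to study design are implemented. SAP 6.1 offers no replacement for the power figure it labels as original.

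Three stronger readings are tempting and not supported:

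- **That the documents conflict in more than half of trials.** This is true at HR 1.0 and at 1.4, but not from about 1.07 to 1.35.
- **That the trial may well end on 73 events and go to Phase 3 on an inflated estimate.** At true HR 1.4 the median HR among efficacy stops would indeed be about 1.69. That figure describes the protocol's look; on the SAP's stated timing there is little left to stop.
- **That the protocol rule plainly remains in force.** The documents leave this open, and the Charter is not available to settle it.

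**Conclusion.** The point holds as an unreconciled decision rule and a power figure that does not match the planned test. Trigger and consequence both differ between the documents, and the consequence matters more. The disagreement would affect about 45% to 57% of trials for true HR between 1.0 and 1.4. This assumes a look at 73 events, 2:1 allocation, a normal approximation for log HR, and one HR for the pooled doses on the protocol's endpoint. On the SAP's endpoint the HR may be a different quantity.

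The power gap is about 80% stated against 69% for a single test at two-sided 0.20, assuming 127 events and HR 1.4 also apply to the SAP's endpoint. A reader might infer that dropping the stops can only help, since power would rise to about 83%. That holds only if a one-sided 0.20 test is intended, whereas SAP 6.2 specifies two-sided. With no efficacy stop, the 0.186 level no longer follows from any boundary calculation.

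**What to change.** Amend the Protocol synopsis and sections 3.1.1, 4.5, 8.1 and 8.7 to match SAP 6.2.1: one look when 120 patients have 28 days of follow-up, with no stopping on efficacy results. Delete the 1.45 and 1.0 rules and the 0.186 final level, and write the DMC Charter to the same rule. In SAP 6.1, restate power for the single-look test and name its sidedness: about 69% for HR 1.4 with 127 events at two-sided 0.20, or about 83% if one-sided 0.20 is intended, in which case SAP 6.2 must say so. The DMC's authority to stop for safety is unaffected.

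The cost is a protocol amendment with IRB/EC approval across up to 60 sites, alignment of the Charter, and a less favourable stated power. No new patients or data are needed.
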